##  Part 2

 ANC ≥0.5×10^9/L and platelet count ≥50×10^9/L unless due to disease involvement in the bone marrow (Part 2 only).

#### Additional Part 2 disease entry criteria including those listed in Part 1 above

- 6) DLBCL (GCB): Confirmed diagnosis of DLBCL with disease characterized as GCB subtype by immunohistochemistry (Hans 2004; Choi 2009) and meeting the rest of the criteria as defined above, including characterization as de novo DLBCL.
- 7) If the subject has MCL, it is characterized by documentation of monoclonal B cells that have a chromosome translocation t(11;14)(q13;q32) and/or overexpress cyclin D1.
- 8) Richter's syndrome: Confirmed diagnosis of and biopsy-proven DLBCL due to Richter transformation and meeting the rest of the criteria as defined above.
- 9) MM: Confirmed diagnosis of MM, which has relapsed after, or been refractory to ≥3 prior therapies for MM, and is progressing at the time of study entry and meeting the rest of the criteria as defined above. Must be able to provide archival or newly obtained bone marrow aspirate/biopsy material for biomarker analysis.
- 10) WM: Confirmed diagnosis of WM, which has relapsed after, or been refractory to ≥1 prior therapy for WM, and is progressing at the time of study entry and meeting the rest of the criteria as defined above. Must be able to provide archival or newly obtained bone marrow aspirate/biopsy material for biomarker analysis.
- 11) Other B-cell malignancy (including but not limited to Hodgkin's lymphoma, Burkitt lymphoma, marginal zone lymphomas, mediastinal large B-cell lymphoma, and hairy cell leukemia): Confirmed diagnosis of previously treated B-cell malignancy and meeting the rest of the criteria as defined above.

#### Part 3 (Under Amendment 3 of this protocol, Part 3 is closed to enrollment.)

- 12) Diagnosis of primary MF, post-polycythemia vera MF, or post-essential thrombocythemia MF.
- 13) Intermediate-1, intermediate-2, or high-risk MF per Passamonti 2010 criteria and must have failed therapy with ruxolitinib.
- 14) Thrombocytopenia (platelet count ≤100×10^9/L at any time after signing informed consent) OR anemia (hemoglobin ≤8.0 g/dL). Subjects who are platelet or red blood cell transfusion-dependent are eligible; platelet counts must be ≥30×10^9/L during the screening period.
- 15) Palpable splenomegaly  $\geq$ 5 cm on physical examination.
- 16) Total Symptom Score ≥13 on the MPN-SAF TSS, not including the inactivity question.
- 17) No splenic irradiation within 6 months before first study dose.
- 18) No myelofibrosis therapy, including any erythropoietic or thrombopoietic agents, within 2 weeks before first study dose.
- 19) ANC ≥0.5×10^9/L.
- 20) Bone marrow blasts <10%.

#### All Parts

- 21) Men and women  $\geq$ 18 years of age on day of signing informed consent.
- 22) Documented active disease.
- 23) ECOG performance status of  $\leq 1$ .
- 24) Completion of all therapy (including surgery, radiotherapy, chemotherapy, immunotherapy, or investigational therapy) for the treatment of cancer ≥4 weeks before the start of study therapy (Parts 1 and 2) and recovered (i.e., Grade ≤1 or baseline) from AEs associated with prior cancer therapy (all subjects). Note: Subjects with Grade ≤2 neuropathy or Grade ≤2 alopecia are an exception to the latter criterion and may qualify for the study.
- 25) Women who are sexually active and can bear children must agree to use highly effective methods of contraception during the study and for 2 days after the last dose of

acalabrutinib or 120 days after the last dose of pembrolizumab, whichever is longer. Note: Highly effective methods of contraception are defined in Section 3.10.9.

- 26) Men who are sexually active and can beget children must agree to use highly effective methods of contraception during the study and for 120 days after the last dose of pembrolizumab. Note: Highly effective methods of contraception are defined in Section 3.10.9.
- 27) Men must agree to refrain from sperm donation during the study and for 120 days after the last dose of pembrolizumab.
- 28) Able to provide tissue, if available, from either an archived or newly obtained tumor sample (most recent biopsy) for biomarker and correlative analysis as appropriate for a given histology.
- 29) Willing and able to participate in all required evaluations and procedures in this study protocol including swallowing capsules without difficulty.
- 30) Ability to understand the purpose and risks of the study and provide signed and dated informed consent and authorization to use protected health information (in accordance with national and local patient privacy regulations).

## 3.3.2 Exclusion Criteria

Subjects will be ineligible for this study if they meet **any** of the following criteria:

## All Parts

- Prior malignancy, except for adequately treated basal cell or squamous cell skin cancer, in situ cancer, or other cancer from which the subject has been disease free for ≥2 years.
- 2) A life-threatening illness, medical condition or organ system dysfunction which, in the investigator's opinion, could compromise the subject's safety, interfere with the absorption or metabolism of acalabrutinib, or put the study outcomes at undue risk.
- 3) Significant cardiovascular disease such as uncontrolled or symptomatic arrhythmias, congestive heart failure, or myocardial infarction within 6 months of screening, or any Class 3 or 4 cardiac disease as defined by the New York Heart Association Functional Classification, or QTc >480 msec at screening.

- 4) Malabsorption syndrome, disease significantly affecting gastrointestinal function, or resection of the stomach, or extensive small bowel resection that is likely to affect absorption, symptomatic inflammatory bowel disease, partial or complete bowel obstruction, or gastric restrictions and bariatric surgery, such as gastric bypass.
- 5) CNS involvement by lymphoma/leukemia.
- 6) Any therapeutic antibody within 4 weeks of first dose of study drug.
- 7) Any prior irreversible BTK inhibitor therapy. Note: Prior treatment with reversible, noncovalent BTK inhibitors is not excluded on this protocol.
- Prior therapy with an anti-PD-1, anti-PD-L1, anti-PD-L2, anti-CD137, or anti-CTLA-4 antibody (including ipilimumab, tremelimumab, or any other antibody or drug specifically targeting T-cell co-stimulation or checkpoint pathways).
- 9) Receiving ongoing immunosuppressive therapy, including systemic or enteric corticosteroids except for minimally systemically absorbed treatments (such as inhaled or topical steroid therapy for asthma, chronic obstructive pulmonary disease, or allergic rhinitis) within 7 days before the first dose of pembrolizumab.
- Active autoimmune disease that has required systemic treatment in past 2 years (i.e., with use of disease modifying agents, corticosteroids or immunosuppressive drugs).
   Note: Replacement therapy (e.g., thyroxine, insulin, or physiologic corticosteroid replacement therapy for adrenal or pituitary insufficiency) is not considered a form of systemic treatment.
- 11) History of interstitial lung disease or non-infectious pneumonitis that required steroids or current pneumonitis.
- 12) History of severe allergic, anaphylactic, or other hypersensitivity reactions to chimeric or humanized antibodies or fusion proteins.
- 13) History of bleeding diathesis (e.g., hemophilia or von Willebrand disease).
- 14) Prior allogeneic hematopoietic stem cell transplantation (HSCT) within the last 5 years.
- 15) Requires treatment with a strong CYP3A inhibitor/inducer.
- 16) Requires or receiving anticoagulation with warfarin or equivalent vitamin K antagonists (e.g., phenprocoumon) within 7 days of first dose of study drug.
- 17) Requires treatment with a proton-pump inhibitor (e.g., omeprazole, esomeprazole, lansoprazole, dexlansoprazole, rabeprazole, or pantoprazole).
- 18) Known history of HIV or active infection with HCV or HBV or any uncontrolled active systemic infection.

- 19) Major surgery within 28 days of first dose of study drug. Note: If a subject had major surgery, they must have recovered adequately from any toxicity and/or complications from the intervention before the first dose of study drug.
- 20) Has received a live vaccine within 30 days of planned start of study therapy.
- 21) History of stroke or intracranial hemorrhage within 6 months before the first dose of study drug.
- 22) Active bleeding that requires hospitalization during the screening period.
- 23) Total bilirubin >1.5×ULN; AST or ALT >3.0×ULN.
- Estimated creatinine clearance of <30 mL/min, calculated using the formula of Cockcroft and Gault [(140-Age) • Mass (kg)/(72 • creatinine mg/dL); multiply by 0.85 if female].
- 25) Breastfeeding or pregnant or expecting to conceive or father children within the projected duration of the trial, starting with the screening visit through 120 days after the last dose of trial treatment.
- 26) Is currently participating in a clinical trial and receiving study therapy or has participated in a study of an investigational agent and received study therapy or used an investigational device within 4 weeks of the first dose of treatment.
- 27) Immediate family members of the sponsor personnel or site staff directly involved with the conduct of this protocol are excluded from participating on this study.
- Presence of a gastrointestinal ulcer diagnosed by endoscopy within 3 months before screening.
- 29) Active or known tuberculosis infection. Note: Tuberculosis testing is not required for this protocol.
- 30) Serologic status reflecting active hepatitis B or C infection:
  - a) Subjects who are anti-HBc positive and who are surface antigen negative will need to have a negative PCR result before enrollment. Those who are HBsAg positive or hepatitis B PCR positive will be excluded.
  - b) Subjects who are hepatitis C antibody-positive will need to have a negative PCR result before enrollment. Those who are hepatitis C PCR positive will be excluded.

## 3.3.3 Replacement of Subjects

Subjects will not be replaced on this study except if needed to complete the DLT assessment in Part 1 (N=6). However, subjects who discontinue from the study due to a DLT during the DLT assessment period will not be replaced.

# 3.3.4 Enrollment Procedures

Enrollment of a subject into the study will be performed according to the following procedure:

- The study center will notify the sponsor when a clinically eligible subject is identified and is ready to screen, to ensure enrollment availability on the study.
- After the subject has signed and dated the (ICF), all screening procedures have been completed, and eligibility has been confirmed, the subject can be officially enrolled into the study.
- To enroll a subject, the study center will fax/email a completed Enrollment Confirmation Form to the sponsor. The enrollment date will be the date that the sponsor confirms enrollment.
- The sponsor will aim to fax/email a completed Enrollment Confirmation Form to the study center within 24 hours.

Treatment must begin within the screening window (see Section 4.1) and after the site has received the Enrollment Confirmation Form from the sponsor.

# 3.4 STUDY DRUGS

## 3.4.1 Premedications

No specific premedications or supporting medications are required in conjunction with acalabrutinib or pembrolizumab administration.

Events of tumor lysis syndrome, consistent with disease-related events, have been reported in subjects exposed to acalabrutinib in both monotherapy and in combination with other agents (acalabrutinib IB). Whether there could be an increased likelihood of tumor lysis syndrome when co-administering acalabrutinib and pembrolizumab is unknown. Investigators are at liberty to consider additional monitoring and prophylaxis for tumor lysis syndrome according to local practices (see Section 3.9). As general precautions considering the subject population, institution of antibiotic prophylaxis for *Pneumocystis (carinii) jiroveci* and use of intravenous immunoglobulin (Ig) may be considered in selected study subjects (see Section 3.9.1).

# 3.4.2 Formulation, Packaging, and Storage

## Acalabrutinib

Acalabrutinib is manufactured according to cGMP regulations and will be provided to the investigational site by Acerta Pharma or designee. Acalabrutinib should be stored according to the instructions on the label that is affixed to the package of the drug product. Acalabrutinib will be provided in white, high-density polyethylene bottles.

If a drug shipment arrives damaged, or if there are any other drug complaints, a Product Complaint Form should be completed and emailed or faxed to the sponsor or the sponsor's representative. Refer to the acalabrutinib IB for additional information regarding the drug products to be used in this trial.

## Pembrolizumab

Pembrolizumab clinical supplies will be provided by the sponsor as summarized in Table 1.

Product Name and Potency	Dosage Form	
MK-3475 50 mg	Lyophilized Powder for Injection	
MK-3475 100 mg/ 4mL	Solution for Injection	

Information on the formulation, packaging and storage of pembrolizumab is provided in the pembrolizumab Pharmacy Manual and the pembrolizumab (MK-3475) Investigator Brochure.

# 3.4.3 Administration of Study Drug

Investigators are prohibited from supplying acalabrutinib to any subjects not properly enrolled in this study. The investigator must ensure that subjects receive acalabrutinib or pembrolizumab only from personnel who fully understand the procedures for administering the drugs. Acalabrutinib 100 mg is intended to be administered orally BID with 8 ounces (approximately 240 mL) of water (avoid grapefruit juice and Seville orange juice due to CYP3A inhibition). Doses should be administered 12 hours apart (a window of ±1 hour is allowed). Acalabrutinib can be taken with or without food. The capsules should be swallowed intact. Subjects should not attempt to open capsules or dissolve them in water.

If a dose is not taken within the allowed window, it can be taken up to 3 hours after the scheduled time with a return to the normal schedule the same or following day. If it has been >3 hours, the dose should not be taken and the subject should take the next dose at the next scheduled time the next day. The missed dose will not be made up and must be returned to the site at the next scheduled visit.

Guidance on co-administration of acalabrutinib with agents that affect gastric pH is provided in Section 3.10.7.

Pembrolizumab will be administered as a dose of 200 mg using a 30-minute IV infusion. Sites should make every effort to target infusion timing to be as close to 30 minutes as possible. However, given the variability of infusion pumps from site to site, a window between -5 minutes and +10 minutes is permitted (i.e., infusion time is 30 minutes -5 minutes/ +10 minutes). Detailed information on preparation of pembrolizumab for infusion is provided in the pembrolizumab (MK-3475) Pharmacy Manual.

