# 3.4.4 Assuring Subject Compliance

For treatments that are taken in the clinic, subjects should take the dose from the drug dispensed for them for that particular time period. All other acalabrutinib treatments will be taken at home. Subjects will receive a drug diary to record the specific time each dose was taken and to record reasons for any missed doses.

Pembrolizumab infusions will be administered only at the clinics per the study schedule. Missed doses of pembrolizumab should not be made up, with the next dose occurring in agreement with the original schedule (from the first dose of drug administered to the subject) for this agent (every 3 weeks).

Subject compliance with acalabrutinib dosing will be assessed at every visit. The subject will be instructed to bring the diary and any remaining capsules to the clinic at their next visit. The study staff will review the diary and ask the subject if all of the capsules were administered. Any remaining or returned capsules will be counted and recorded as

described in Section 7.6. Returned capsules must not be redispensed. Only a sufficient quantity of capsules will be dispensed to reach the next protocol-specified visit unless approved by the medical monitor. Subjects on treatment who are on yearly visits (see Appendix 5) may return to the clinic to receive a 6-month supply between yearly visits, if they are unable to get a 1-year supply at a time.

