## 3.8.1 Dose Modifications for Acalabrutinib

After the DLT review is cleared, the actions in Table 2 should be followed for the following toxicities:

- Grade 4 neutropenia (<500/µL) for >7 days (neutrophil growth factors are permitted per American Society of Clinical Oncology [ASCO] guidelines [Smith 2015] and use must be recorded on the case report form [CRF]).
- Grade 3 thrombocytopenia in presence of significant bleeding.
- Grade 4 thrombocytopenia.
- Grade 3 or 4 nausea, vomiting, or diarrhea, if persistent despite optimal antiemetic and/or anti-diarrheal therapy.
- Any other Grade 4 toxicity or unmanageable Grade 3 toxicity.

 Table 2
 Drug Discontinuation Actions for Acalabrutinib

Occurrence	Action
1 st - 2 nd	Hold acalabrutinib until recovery to Grade ≤1 or baseline; may restart at original dose level
3 rd	Hold acalabrutinib until recovery to Grade ≤1 or baseline; restart at one dose level lower (100 mg QD)
4 th	Discontinue acalabrutinib

If acalabrutinib is reduced for apparent treatment-related toxicity, the dose need not be re-escalated, even if there is minimal or no toxicity with the reduced dose. However, if the subject tolerates a reduced dose of acalabrutinib for  $\geq$ 28 days then the dose may be increased to the next higher dose level, at the discretion of the investigator. Such

re-escalation may be particularly warranted if further evaluation reveals that the AE that led to the dose reduction was not treatment-related. However, the maximum dose of acalabrutinib is 100 mg BID for this protocol.

Treatment with acalabrutinib should be withheld for any unmanageable, potentially study drug-related toxicity that is Grade  $\geq$ 3 in severity. Any other clinically important events where dose delays may be considered appropriate by the Investigator must be discussed with the medical monitor. Study drug may be withheld for a maximum of 28 consecutive days from expected dose due to toxicity. Study treatment should be discontinued in the event of a toxicity lasting >28 days, unless reviewed and approved by the medical monitor.

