# 5.0 STATISTICAL METHODS OF ANALYSIS

# 5.1 GENERAL CONSIDERATIONS

Descriptive statistics (including means, standard deviations, and medians for continuous variables and proportions and CIs for discrete variables) will be used to summarize data as appropriate. As appropriate, analyses will be performed by cancer type or overall. Depending on Part 1 and the number of expansion cohorts opened in Parts 2 and 3, a total of 6 to 324 evaluable subjects will be enrolled in this study. Under Amendment 4 of this protocol, the planned total enrollment was approximately 160 evaluable subjects; enrollment was closed in May 2017 with a total of 161 evaluable subjects.

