# 5.5.3 Study Treatment Administration and Compliance

Descriptive information will be provided regarding the number of acalabrutinib and pembrolizumab doses prescribed, the total number of doses taken, the number of days of treatment, and the number and timing of prescribed dose reductions and interruptions.

For each subject, acalabrutinib and pembrolizumab compliance will be described in terms of the relative dose intensity.

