9.5.3 Exposure to Study Drug

Descriptive statistics (n, mean, standard deviation, median, and range) will be used to summarize regarding the number of acalabrutinib doses prescribed:

- Total number of doses taken
- Duration of exposure (the interval between first dose date and last dose date)
- Average daily dose (the ratio of total dose administered and treatment duration)
- Relative dose intensities (the ratio of average daily dose and prescribed doses)
- The number and timing of prescribed dose reductions and interruptions

Descriptive statistics (n, mean, standard deviation, median, and range) will be used to summarize regarding the number of acalabrutinib doses prescribed:

- Total number of doses taken
- Duration of exposure (the interval between first dose date and last dose date)
- Average dose per cycle (total dose administered per cycle)
- Relative dose intensities (the ratio of average daily dose and prescribed doses)
- The number and timing of prescribed dose reductions and interruptions
-

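### The missed-dose rule sends a subject who misses a morning acalabrutinib dose to the next day, although the next twice-daily dose is due that evening

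*Protocol*

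**What the plan says.** Section 3.4.3 (Administration of Study Drug) sets acalabrutinib at 100 mg twice daily: "Doses should be administered 12 hours apart (a window of ±1 hour is allowed"). A dose outside that window may still be taken up to 3 hours after its scheduled time, and the subject then returns to the usual schedule on the same or the following day. Beyond 3 hours, "the dose should not be taken and the subject should take the next dose at the next scheduled time the next day". The section continues: "The missed dose will not be made up and must be returned to the site at the next scheduled visit".

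The rule does not separate morning from evening doses. Section 3.5 repeats the 100 mg twice-daily regimen. The only once-daily schedule is the dose reduction in Table 2 of Section 3.8.1, after a third occurrence of a listed toxicity.

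Apart from doses taken in the clinic, "All other acalabrutinib treatments will be taken at home" (Section 3.4.4). For the analysis, Section 5.5.3 states that "acalabrutinib and pembrolizumab compliance will be described in terms of the relative dose intensity". SAP Section 9.5.3 defines relative dose intensity as the ratio of the average daily dose to the prescribed dose.

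**The concern.** On a 12-hourly schedule, the next scheduled time after a morning dose is that evening. The rule asks for the next scheduled time and also for the next day. After a missed morning dose a subject cannot do both.

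A subject who follows the words about the day skips the evening dose as well, so one late dose becomes two omitted doses. A subject who follows the words about the schedule takes the evening dose. Subjects managing their own dosing at home could settle the conflict differently.

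What is at stake is exposure, and with it the relative dose intensity that the plan reports. No hypothesis test, sample size or endpoint definition depends on this sentence.

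**Working it through.** The plan gives no figure to reproduce, so the check compares the rule with the schedule and then counts doses.

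**Inputs**
- 100 mg twice daily, 12 hours apart, with a 3-hour limit for a late dose (Section 3.4.3).
- Relative dose intensity as average daily dose over prescribed dose (SAP 9.5.3).
- Clock times of 08:00 and 20:00. These are assumed; the documents give none.

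**Rule against schedule**

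| Dose skipped | Next scheduled time | Is that the next day? |
|---|---|---|
| Evening (20:00), twice daily | 08:00 tomorrow | Yes, the rule is consistent |
| 100 mg once daily | Same time tomorrow | Yes, the rule is consistent |
| Morning (08:00), twice daily | 20:00 today | No, the rule contradicts itself |

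**Size of one event** (08:00 dose on day 1 skipped; last dose taken at 20:00 on day 0)

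| | Literal rule | Evening dose taken |
|---|---|---|
| Next dose taken | 08:00, day 2 | 20:00, day 1 |
| Gap between doses taken | 36 h | 24 h |
| Doses omitted | 2 | 1 |
| Dose received on day 1 | 0 of 200 mg | 100 of 200 mg |

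The literal rule therefore costs 1 extra dose and 36 − 24 = 12 extra hours.

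**Effect on relative dose intensity.** With one skipped morning dose in D days there are 2D prescribed doses:
- literal rule: (2D − 2)/2D
- evening dose taken: (2D − 1)/2D
- difference: 1/(2D)

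| D (assumed) | Literal rule | Evening dose taken | Difference (from unrounded values) |
|---|---|---|---|
| 84 days | 166/168 = 98.8% | 167/168 = 99.4% | 0.6 points |
| 28 days | 54/56 = 96.4% | 55/56 = 98.2% | 1.8 points |
| 7 days | 12/14 = 85.7% | 13/14 = 92.9% | 7.1 points |

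The documents give no missed-dose rate, so D is illustrative. The table also assumes that the literal reading is followed every time.

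**What was probably intended.** Two neighbouring sentences point to a slip. The one on doses up to 3 hours late allows a return to schedule on the same day, and the one that follows the rule speaks of a single missed dose. No reason is given for omitting two.

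**The case against.** The strongest reply is that the harmful reading is the weaker one. The section says twice daily, 12 hours apart, next scheduled time, and one missed dose, so a sensible site would have the subject take the evening dose. What subjects are actually told sits in a diary that is not in the documents. This stands as a limit on the consequence: a wording conflict is shown, an effect on dosing is not. It does not make the sentence correct, because taking the evening dose means departing from what the sentence says.

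A second reply is that the clinical weight is small. The protocol accepts holds of 3 days before and after major surgery (Section 3.10.8), interruption for short courses of CYP3A inhibitors of up to 7 days (Section 3.10.7), and up to 28 consecutive days for toxicity (Section 3.8.1). This also stands, although those interruptions have a purpose and this one has none.

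A third reply is that the compliance data are not distorted. Relative dose intensity falls, correctly, when doses are not taken, and Section 3.4.4 also checks compliance at each visit by diary review, questioning and capsule count. That is right. The literal rule would lower exposure itself; it would not bias how exposure is reported.

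Finally, "enrollment was closed in May 2017 with a total of 161 evaluable subjects" (Section 5.1), so the reach is limited. But the current text was written after that closure. Section 3.6 lets acalabrutinib continue until 48 months after the last enrollment, with possible continued access within the study after that.

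**Conclusion.** The concern holds. For a missed morning dose on the standard regimen the rule is wrong as written, and neither document corrects it. Followed literally, each such event costs one extra dose (100 mg) and 12 extra hours without drug.

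The per-event figures depend only on the 12-hour schedule; the clock times are for illustration. The cumulative effect is unknown. A difference of 0.6 points in relative dose intensity needs one skipped morning dose per 84 days, and 7.1 points needs one every week, a rate for which the documents offer no support. No loss of efficacy or safety is shown. This is a clear error in a working dosing instruction, with a modest effect, and it should be corrected.

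**What to change.** In Section 3.4.3, delete *the next day* from the end of the rule, so that after a skipped dose the subject takes the next dose at the next scheduled time. That is correct for a missed morning dose, a missed evening dose and 100 mg once daily. Check that the subject diary instructions say the same.

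The cost is three words. A protocol change needs an amendment submitted to the IRB/IEC (Sections 7.1 and 7.8), so it can go with the next amendment made for other reasons. It adds no procedures or visits and changes nothing in the SAP.
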